C _{ss,min}	Minimum observed plasma concentration at steady state
CSR	Clinical Study Report
C _{trough}	Pre-dose Trough Concentration
CV	Coefficient of Variation
DBP	Diastolic blood pressure
ECG	12-Lead Electrocardiogram
eCRF	Electronic Case Report Form
FE	Food Effect
FSH	Follicle-stimulating hormone
GCP	Good Clinical Practice
HIV	Human Immunodeficiency Virus
MAD	Multiple-ascending dose
MedDRA	Medical Dictionary for Regulatory Activities
N/A	Not Applicable
NCS	Not Clinically Significant
NK	Not Known
PI	Principal Investigator
PD	Pharmacodynamic
PK	Pharmacokinetic
PT	Preferred Term
QTcB	QT interval with Bazett's correction method
QTcF	QT interval with Fridericia's correction method
R _{acc}	Accumulation ratio
SAD	Single Ascending Dose
SAE	Serious Adverse Event
SAP	Statistical Analysis Plan
SBP	Systolic blood pressure
SD	Standard Deviation
S.I.	International System of Units

Abbreviation	Description
SOC	System Organ Class
SOP	Standard Operating Procedure
SRC	Safety Review Committee
$t_{1/2z}$	Terminal elimination half-life
TEAE	Treatment Emergent Adverse Event
T_{max}	Time to maximum concentration
$T_{ss, max}$	Time for C_{max} at steady state.
V_z/F	Apparent volume of distribution after extravascular administration
V_z/F_{ss}	Apparent volume of distribution after extravascular administration at steady state
WHO-DD	World Health Organization Drug Dictionary

1. INTRODUCTION

The following Statistical Analysis Plan (SAP) provides the outline for the statistical analysis of the data collected from the [CVN766-101](#) study (protocol version 4.0 amendment 3 dated 19 May 2022).

The planned analyses identified in this SAP may be included in clinical study reports (CSRs), regulatory submissions, or future manuscripts. Also, post hoc exploratory analyses not necessarily identified in this SAP may be performed to further examine study data. Any post hoc, or unplanned exploratory analyses performed will be clearly identified as such in the final CSR.

CVN766 is a highly selective orexin-1 receptor (Ox1R) antagonist and may have utility as treatment for psychiatric disorders including schizophrenia, panic disorder and anxiety, and addiction. The present study will be the first conducted in humans with CVN766 and will examine the compound's safety, tolerability, and PK in healthy subjects.

2. PROJECT OVERVIEW

2.1 Study Design

This is a Phase 1, randomized, double-blind, placebo-controlled, single- and multiple-dose ascending study in healthy subjects with concurrent PK sampling from blood plasma, urine, and cerebrospinal fluid. This study is formed by two parts: Part 1 (SAD) and Part 2 (MAD).

2.1.1 Part 1: SAD is the single-dose regimen and Fasted- Fed Crossover

Approximately 40 healthy male or female subjects will be enrolled in 1 of 5 single-dose cohorts (designated as S1 through S5, respectively) in an ascending fashion. An optional Cohort 3a may be added in parallel to SC3 for additional safety and tolerability evaluation. Cohort S3a dose level will be consistent with Cohort S3 (45 mg planned) in a fasted condition only and without lumbar puncture, aligned with other SAD cohorts. Each cohort will consist of 8 subjects randomized to CVN766 or placebo, whereby 6 subjects will receive a single oral dose of CVN766 suspension, and 2 subjects will receive a matching placebo suspension under overnight fasted conditions. Sentinel dosing (1 subject to receive CVN766 and 1 subject to receive placebo) will be used in each cohort to ensure adequate safety and tolerability evaluation prior to administering CVN766 or placebo to the remainder of the subjects within the cohort. The planned dose levels will be 5, 15, 45, 125, and 250 mg CVN766. Each following dose level may be higher, lower, or remain the same as the preceding cohort. Additional cohort(s) may be added if deemed necessary by the SRG to fully characterize the safety and tolerability of CVN766. To assess the effect of food on CVN766 bioavailability in suspension formulation, the single-dose administration will be repeated in a single cohort (S3) after ingestion of a standardized high-fat, high-calorie meal. Once the safety of the S3 cohort dose level has been assessed, the S3 cohort subjects will return to the clinic (no sooner than 14 days after their prior dose, or at least 4 half-lives, has lapsed based on preliminary PK data, whichever is longer). They will receive the same dose as before, administered after ingesting a standardized breakfast. Subjects will finish at least approximately 85% of their breakfast within 30 minutes and receive an investigational product 30 minutes (\pm 5 minutes) after beginning the meal. Sentinel dosing will not be required for subjects returning to the clinic for the fed regimen. If the CVN766 PK parameters in the fasted S3 cohort reveal poor absorption with inconclusive results, the fed cohort will be deferred until a higher dose level.

[figure not shown]
On Day 1, subjects will undergo safety monitoring and PK sampling from blood plasma through 72 hours post-dose and, for cohort S3 (fasted) only, from CSF via lumbar puncture at 3 hours post-dose

2.1.2 Part 2 MAD is a Multiple-Dose Regimen

Approximately 24 healthy male and female subjects aged 18 to 55 will be enrolled in 1 of the 3 multiple-dose cohorts (designated as M1 through M3, respectively) in an ascending fashion. The dose levels planned to be studied in the multiple-dose regimen are 45, 125, and 250 mg CVN766 for multiple-dose cohorts M1 through M3, respectively. Each multiple-dose cohort will consist of 8 subjects randomized to CVN766 or placebo, whereby 6 subjects will receive a daily oral dose of CVN766, and 2 subjects will receive matching placebo for 7 days. Dosing will be administered in the fasting state; the SRG can change this if exposure is higher in the fed state. The planned dosing duration for the multiple-dose cohorts is 7 days. However, the duration may be increased to \leq 14 days if preliminary PK data suggest steady-state will not be achieved within 6 days of daily dosing.

On Day 1 subjects, will undergo safety monitoring and PK sampling from blood plasma through 24 hours post-dose and on Day 7, will undergo safety monitoring and PK sampling from blood plasma through 72 hours post-dose. Additionally, PK samples will be collected on Days 3, 4, 5 and 6 prior to the next planned dose. For cohort M1, on day 7 only, subjects will undergo PK sampling from CSF via lumbar puncture at 3 hours post dose and PK sampling from urine over 24 h on Day 1 and Day 7. CSF samples may also be taken from M2 and M3 cohorts at the SRG's discretion.

Figure 1: Study Design

2.2 Objectives

Primary objective(s)

- To characterize the safety and tolerability profile of escalating dose levels of CVN766 suspension when administered as a single oral dose or daily oral doses for 7 days in healthy subjects.

Secondary objective(s)

The secondary objectives of this study are:

- To characterize the single-dose PK profile of CVN766 in plasma, and CSF
- To characterize the multiple-dose PK profile of CVN766 in plasma, and CSF
- To assess the effect of food on the bioavailability of CVN766 in the current formulation

Exploratory objective(s)

The exploratory objectives of this study are:

- To explore possible drug metabolic enzyme and transporter polymorphisms that may contribute to variability in CVN766 PK, or safety

2.3 Endpoints

Primary endpoint(s)

The primary endpoints of this study will be the following:

- Percentage of subjects who experience at least one treatment-emergent adverse event (TEAE)
- Percentage of subjects with abnormal and clinically significant (CS) safety laboratory test results at least once post-dose
- Percentage of subjects with abnormal and CS electrocardiogram (ECG) test results at least once post-dose
- Percentage of subjects with abnormal and CS vital sign measurements at least once post dose

Secondary endpoints(s)

- Single-dose plasma PK parameters of CVN766 including time to maximum plasma concentration (T_{max}), area under the plasma concentration-time curve from time 0 to 24 (AUC_{24}) and time 0 to infinity (AUC_{inf}), and terminal elimination half-life ($t_{1/2z}$) Multiple-dose plasma PK parameters of CVN766 including C_{min} , C_{trough} , C_{max} , AUC from time 0 to the end of dosing interval (AUC_t), terminal elimination half-life ($t_{1/2z}$), accumulation ratio (R_{acc}), time to steady-state ($T_{ss,max}$), steady-state C_{max} ($C_{max,ss}$), and steady-state C_{min} ($C_{min,ss}$) Single-dose and multiple-dose CSF concentrations and CSF: plasma ratios of CVN766

Other endpoints(s)

- Change from baseline in safety laboratory and ECG test results and vital signs.
- Additional plasma PK parameters of CVN766: CL/F or CL/F_{ss} and Vz/F or Vz/F_{ss}

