Part 2 – Multiple Ascending Doses

All PK analyses, PK summary tables and figures will be based on the PK set. All analyses will be summarized as described in section 3.1 (PK - continuous descriptive analysis). All listings will be based on the PK set. All missing and BLQ handling of urine concentrations for PK analysis will be based on section 3.5.

Approximate attainment of steady state will be visually assessed by plotting mean C_{trough} concentrations.

The following pharmacokinetic parameters will, where possible, be determined from the plasma concentrations and CSF of analyte using non-compartmental methods via Phoenix WinNonlin Version 8.3 or higher.

Parameter at	Definition
Day 1	
C _{max}	Observed maximum CVN766 concentration in the dosing interval at Day 1
C _{min} ,	Observed minimum CVN766 concentration in the dosing interval at Day 1
C _{trough DayN}	Plasma concentration at the end of the dosing interval at day N, where N is Day 2,3,4,5,6,or 7
T _{max}	Time to reach maximum CVN766 concentration at Day 1
T _{min}	Time of minimum observed CVN766 concentration at Day 1
AUC _t	Area under the drug concentration-time curve, from time 0 (time of dosing) to the last measurable concentration at steady state using 'linear trapezoidal/ linear interpolation method' when t is < 24h. Determined following Dose on Day 7
AUC ₂₄	The area under the plasma CVN766 concentration-time curve, from time 0 to 24 hours, calculated by linear trapezoidal/ linear interpolation method. Determined following Dose on Day 1
CSF:Plasma ratio:	Ratio of the CVN766 concentration in CSF vs the CVN766 concentration in plasma at 3 h post dose
DN_C _{max,ss}	Dose-normalized C _{max,ss} = C _{max,ss} /dose
DN_AUC _{24hr}	Dose-normalized AUC _{24hr} = AUC _{24hr} /dose
DN_AUC _t	Dose-normalized AUC _t = AUC _t /dose

Parameter at Day 7	Definition
$C_{\max, ss}$	Observed maximum CVN766 concentration in the dosing interval at steady state at Day 7.
$C_{\min, ss}$	Observed minimum CVN766 concentration in the dosing interval at steady state at Day 7.
$C_{\text{trough Day}N}$	Plasma concentration at the end of the dosing interval at day N, where N is Day 2,3,4,5,6, or 7
$C_{\text{avg}, ss}$	Average steady state CVN766 concentration, determined following Dose on Day 7, using the following formula $C_{\text{avg}, ss} = \text{AUC}_{\text{tau}} / \text{tau}$ Where, tau = dosing interval
$T_{\max, ss}$	Time to reach maximum CVN766 concentration in the dosing interval at steady state at Day 7.

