$\text{DN}_{\text{AUC}_{\text{tau}}}$	Dose-normalized $\text{AUC}_{\text{tau}} = \text{AUC}_{\text{tau}}/\text{dose}$
$\text{DN}_{\text{AUC}_{\text{inf}}}$	Dose-normalized $\text{AUC}_{\text{inf}} = \text{AUC}_{\text{inf}}/\text{dose}$

 C_{trough} determination for MAD cohorts:

C _{trough_Day1}	The pre-dose morning concentration observed on day 2 prior to the next dosing
C _{trough_Day2}	The pre-dose morning concentration observed on day 3 prior to the next dosing
C _{trough_Day3}	The pre-dose morning concentration observed on day 4 prior to the next dosing
C _{trough_Day4}	The pre-dose morning concentration observed on day 5 prior to the next dosing
C _{trough_Day5}	The pre-dose morning concentration observed on day 6 prior to the next dosing
C _{trough_Day6}	The pre-dose morning concentration observed on day 7 prior to the next dosing

C_{trough_Day1}, C_{trough_Day2}, C_{trough_Day3}, C_{trough_Day4}, C_{trough_Day5}, C_{trough_Day6} will be listed for each MAD cohort and dose level.

Additional pharmacokinetic parameters may be determined where appropriate.

Pharmacokinetic analysis will be carried out using actual doses and blood sampling times (post dose hourly sampling times for the specified days), where possible. If actual times are missing, nominal times may be used with sponsor approval.

Plasma, urine, and CSF concentrations of CVN766 will be used as supplied by the bioanalytical laboratory. The units of concentration and resulting PK parameters, with amount or concentration in the unit, will be presented as they are received from the bioanalytical laboratory.

If a PK parameter cannot be derived from a patient's concentration data, the parameter will be coded as NC (i.e., not calculated). NC values will not be generated beyond the day that a patient discontinues. If an individual patient has a known biased estimate of a PK parameter (due for example to a deviation from the assigned dose level and/or concomitant medication violation), this will be footnoted in summary tables and the parameter will not be included in the calculation of summary statistics or statistical analyses.

Pharmacokinetic Noncompartmental Analysis (NCA)

General Plasma NCA Pharmacokinetic Settings

The general settings in Phoenix WinNonlin® for generation of plasma PK parameters are as listed below.

- NCA Model Type: Plasma (200-202)
- Weighting: Uniform
- AUC Calculation Method: Linear trapezoidal/ linear interpolation method
- Dose Options Type: Extravascular

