Summary of Plasma PK parameters

PK parameters will be determined for each analyte with intensive PK samplings. For the purpose of calculating the non-compartmental PK parameters, concentrations that are BLQ prior to the first measurable concentration value will be set equal to zero. BLQ values embedded between measurable concentrations will be set to missing. Concentrations that are BLQ in the terminal phase after the last measurable concentration will be set to missing.

It should be noted the imputation of BLQ for the determination of PK parameters is different from the BLQ imputation when PK concentrations are summarized. When PK parameters are estimated by a standard non-compartmental model, actual collection time will be used in the calculation of plasma PK parameters.

Goodness of Fit

- If data permits, the default ‘best fit’ method by Phoenix WinNonlin will be used for the selection of slopes to determine ‘ λ_z ’. If data do not permit, then the slope selection will be done by visual inspection or by a manual method to determine λ_z .
- When assessing terminal elimination phases, the R^2 adjusted value will be used as a measure of the goodness of fit of the data points to the determined line.
- Regression-based parameters (λ_z or k_{el} , AUC_{inf} , $AUC\%_{extrap}$, $t_{1/2}$, CL/F or CL/Fss, and V_z/F or V_z/F_{ss}) will only be calculated if the R^2 adjusted value of the regression line is greater than or equal to 0.8. If regression-based parameters cannot be calculated, they will be set to “NC”, defined as “not calculated” in the data listings and summary tables as appropriate.

Calculation of AUC

- The minimum requirement for the calculation of AUC will be the inclusion of at least 3 consecutive plasma concentrations above the lower limit of quantification (LLOQ), with at least one of these concentrations following C_{max} .
- All AUC values will be calculated using linear trapezoidal/ linear interpolation method

Period of Estimation

- Time period used for the estimation of $t_{1/2}$, where possible, will be over at least 2 half lives.
- Where an elimination half-life is estimated over a time period of less than 2 half-lives, it will be flagged in the data listings at the discretion of the pharmacokineticist, and the robustness of the half-life value and regression-based parameters (λ_z or k_{el} , AUC_{inf} , $AUC_{\%extrap}$, $t_{1/2}$, CL/F or CL/F_{ss} , and V_z/F or V_z/F_{ss}) should be discussed in the study report.

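### Section 10.7 sets CL/Fss to not calculated on a λz fit that its own formula does not use; the Tss,max wording and the trough day index also need reconciling

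*SAP*

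**What the plan says.** **CL/Fss.** The Day 7 parameter table in SAP section 10.5 defines CL/Fss as dose over AUCtau, and AUCtau as a linear-trapezoid area over one dosing interval. Section 10.7, under Goodness of Fit, puts CL/Fss in a list of regression-based parameters. These are calculated only if the R² "adjusted value of the regression line is greater than or equal to 0.8"; otherwise they are shown as NC. Period of Estimation repeats the same list, as parameters whose robustness is to be discussed when the half-life rests on a short time span. Section 2.3 places CL/Fss among the other endpoints.

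**Time to steady state.** Among the secondary multiple-dose parameters, section 2.3 names "time to steady-state" and attaches the symbol Tss,max. The abbreviation list gives that symbol as "Time for C_{max} at steady state". Section 10.5 derives the matching parameter, Tmax,ss: "Time to reach maximum CVN766 concentration in the dosing interval at steady state at Day 7". On attainment of steady state, section 10.5 says: "Approximate attainment of steady state will be visually assessed by plotting mean" trough concentrations.

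**Troughs.** The parameter tables in section 10.5 define Ctrough DayN as "Plasma concentration at the end of the dosing interval at day N, where N is Day 2,3,4,5,6,or 7". The trough list later in the same section runs from C_trough_Day1 to C_trough_Day6. Its last entry, C_trough_Day6, is "The pre-dose morning concentration observed on day 7 prior to the next dosing".

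**The concern.** A goodness-of-fit gate on λz is sound for anything that contains λz. Applied to a parameter that does not, it deletes values for a reason unrelated to their validity. The deletion is not random: it falls on participants whose late samples (36 to 72 h) scatter, flatten or rebound. With six active participants per cohort, losing one changes the CL/Fss summary visibly.

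The two labels matter for a different reason. Attainment of steady state is a matter of days and Tmax,ss a matter of hours. If words and symbol name different quantities, a reader of the study report cannot tell which secondary endpoint was meant. Ctrough is also a named secondary parameter, and two people following different parts of section 10.5 would put different samples under the same label.

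**Working it through.** The SAP states no figure for this point that could be reproduced. The check is of formulas and labels, with one numerical illustration.

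**1. Which parameters contain λz?** (formulas from 10.5)

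| Parameter | Formula | Uses λz? |
|---|---|---|
| CL/F (single dose) | Dose / AUCinf, with AUCinf = AUCt + Clast/λz | Yes |
| Vz/Fss | Dose / (λz × AUCtau) | Yes |
| CL/Fss | Dose / AUCtau, trapezoid over the interval | No |

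Only CL/Fss is misplaced.

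**2. Illustration.** Assumed, not from the SAP: one compartment at steady state, 45 mg every 24 h, CL/F = 10, half-life 15 h, ka = 1.5/h. Sampling is the Day 7 schedule in 10.2.

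- Undistorted profile: Dose/AUCtau = 9.98 (true value 10; the gap is trapezoid error).
- Multiply only the 36, 48 and 72 h concentrations by 0.5, 2.0 and 2.6. AUCtau stops at 24 h, so CL/Fss stays at 9.98.
- Adjusted R² of the log-linear fit to the last 3, 4, 5, 6, 7, 8 and 9 points: −0.92, 0.08, 0.46, 0.61, 0.70, 0.75, 0.79. The tenth point back is the 2 h sample, which is Cmax in this profile, and 10.7 excludes Cmax from the regression.
- Every permitted fit is below 0.8, so 10.7 reports NC although the calculable value is 9.98.

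The distortion was chosen to trip the rule. It shows the mechanism, not how often it would occur.

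**3. Size of a loss.** Six active participants per multiple-dose cohort (2.1.2), so each NC removes 1/6 = 16.7%. The half-width of a 90% interval for a mean, in SD units with the SD unchanged, is t(0.95, n−1)/√n:

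- n = 6: 2.015/√6 = 0.82
- n = 5: 2.132/√5 = 0.95
- n = 4: 2.353/√4 = 1.18

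The SAP plans no interval for CL/Fss, so these figures only gauge the loss of precision.

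**4. Words against symbol.** Under once-daily dosing, the fraction of steady state after n doses is 1 − 2^(−24n/t½). For assumed half-lives of 15, 24, 36 and 48 h, 90% is first reached at dose 3 (0.964), 4 (0.938), 5 (0.901) and 7 (0.912). A time of peak within one 24 h interval cannot stand for this quantity.

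**5. Trough labels mapped to samples.** Section 10.2 schedules seven end-of-interval samples: pre-dose on Days 2 to 7, and 24 h after the Day 7 dose (Day 8).

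| Source in 10.5 | Labels | Samples (study day) | Interval not covered |
|---|---|---|---|
| Parameter tables, read literally | Day 2 to Day 7 | 3 to 8 | Day 1 |
| Trough list | Day 1 to Day 6 | 2 to 7 | Day 7 |
| Parameter tables, if N is the day of the pre-dose sample | Day 2 to Day 7 | 2 to 7 | Day 7 |

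On the third reading the samples agree with the trough list, but every label is one day out: C_trough_Day2 is the Day 2 sample in one place and the Day 3 sample in the other. No reading makes the two parts of 10.5 agree.

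**The case against.** **A reader might infer that a secondary endpoint is never estimated, or that an hours-scale Tmax would be reported as time to steady state.** The documents do not support that. The SAP's own definition of the symbol is a time of peak, section 2.3 lists it beside steady-state Cmax and Cmin, and the Day 7 table shell labels the row Tmax,ss. No shell has a row for time to steady state. A dropped word in 2.3 is the likelier explanation. What stands is that words and symbol differ and must be reconciled.

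**A reader might infer that the last trough is thrown away.** It is not. The 24 h sample after the Day 7 dose is summarised and listed with the plasma concentrations, ends the AUCtau interval, and falls under N = 7 in the parameter tables. Only the trough list omits it, and that list fits the abbreviation list's description of a trough as a pre-dose value, since no dose follows Day 7 in the planned regimen. What stands is the conflicting index.

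**A reader might say that steady state goes unassessed and needs a model.** Individual and mean trough figures are both planned (section 16), and plots are reasonable in a descriptive Phase 1 plan. A rule that declares steady state once a trough slope's confidence interval includes zero would be worse. One slope over three troughs cannot identify a first day of steady state, and such a rule rewards imprecision. With 6 participants, 3 troughs and an assumed within-participant CV of 15, 25 or 30%, the 90% half-width t(11) × σ/√12 is 0.077, 0.128 or 0.152 per day on the log scale. Estimated rises of up to about 8, 14 or 16% per day would pass.

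**On CL/Fss, the loss is partly recoverable.** Dose-normalised AUCtau is its exact reciprocal, is not on the 10.7 list, and is tabulated for Day 7. CL/Fss also enters no inferential analysis. Both points are right and limit the harm. They also show the inconsistency: the same area would be reported as AUCtau/dose for a participant whose Dose/AUCtau is declared not calculable.

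**Conclusion.** The CL/Fss rule is wrong as written. Followed exactly, it discards valid values selectively for participants with poor terminal fits. Each loss is 1 of 6 in a cohort. The number of losses is unknown because the SAP gives no failure rate, and the direction of any bias cannot be stated in advance. The conclusion assumes that AUCtau can be formed from observed samples through 24 h. If the 24 h value were missing or below quantification, an extrapolation might bring λz in, but the SAP describes none. The weight is moderate, because CL/Fss is an other endpoint and its reciprocal is reported elsewhere.

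The Tss,max wording and the trough index are genuine inconsistencies that should be settled before programming. Neither makes a planned analysis give a wrong number.

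**What to change.** 1. In section 10.7, delete CL/Fss from the regression-based lists under Goodness of Fit and Period of Estimation. Keep Vz/Fss and single-dose CL/F on both.
2. In section 2.3, rename the endpoint Tmax,ss, described as the time of the peak at steady state. Add a sentence that attainment of steady state is assessed descriptively from the individual and mean trough plots.
3. In section 10.5, use one definition in the parameter tables and the trough list: Ctrough DayN is the concentration at the end of day N's dosing interval, for N = 1 to the last dosing day, including the scheduled 24 h sample after the last dose. Indexing to the last dosing day also covers the longer dosing that section 2.1.2 allows. Align the abbreviation list and the shells.
4. If a trough slope with 90% CI is added to the plots, report it as description only, with no rule that declares steady state from it.

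The cost is SAP wording and matching shell labels. Every sample involved is already scheduled, and no new analysis is required.
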